## 9.5 Protocol Deviations

Significant protocol deviations that could potentially affect the efficacy or safety conclusions of the study will be identified prior to database lock and unblinding of individual subject treatment information. Significant protocol deviations may include, but are not limited to:

- Randomly assigned subjects who did not satisfy selected inclusion and exclusion criteria
- Randomly assigned subjects who developed withdrawal criteria during the study but were not withdrawn
- Subjects who were randomized incorrectly including subjects of the same household who are randomized to different treatments
- Subjects who received the wrong treatment
- Subjects where the subject/site staff were improperly unblinded
- Week 12 Lesion Count not performed
- Subjects who received an excluded concomitant treatment.

The decision on the criteria for whether a subject is excluded from the PP Population will be made during the data review meeting prior to unblinding and database lock. Reasons for exclusion of a subject from the analysis will be listed.

A listing of all protocol deviations including the deviation designation (major or minor and significant or not), category, and indication of whether the deviation led to an exclusion of a subject from the PP Population will be presented in a data listing. Additionally, a listing of missed visits due to COVID-19 will be presented.

Major and significant protocol deviations will be summarized by deviation category and treatment group.

## 9.6 Medical History

Medical history verbatim terms in the eCRFs will be mapped to system organ classes and preferred terms using the Medical Dictionary for Regulatory Activities (MedDRA) Version 23.0 or later. Subject incidence of unique medical history terms by MedDRA system organ class and preferred term will be presented. The summary will be ordered by descending order of incidence in the SB206 treatment group of system organ class and preferred term within each system organ class.

## 9.7 Prior and Concomitant Medications

Prior and concomitant medication verbatim terms in the eCRFs will be mapped to anatomical/therapeutic/chemical (ATC) class and preferred names using the WHODrug Global B3 (version March 2020 or later). Prior medications are those medications started prior to the first application of study drug. Concomitant medications are those medications started on or after the date of first application of study drug or medications started prior to initial application of study drug and continued during the study. A medication can be classified as both prior and concomitant. If it cannot be determined whether the medication was a prior (or concomitant) medication due to a partial start or stop date, then it will be counted as both prior and concomitant; see Appendix A for the imputation of missing dates algorithm.

Prior and concomitant medications will be summarized for each treatment by WHODrug Global ATC class Level 3 and preferred name. These summaries will present the number and percentage of subjects using each medication. Subjects may have more than 1 medication per ATC class and preferred name. At each level of subject summarization, a subject is counted once if he/she reported 1 or more medications at that level. Each summary will be ordered by descending order of incidence in the SB206 treatment group of ATC class and preferred name within each ATC class.

## 10. EFFICACY ANALYSES

The primary efficacy analysis will be based on the ITT Population. Additional supportive efficacy analyses will be performed using the PP Population.

## 10.1 Efficacy Endpoints

The primary efficacy endpoint is the proportion of subjects with complete clearance of all treatable MC at Week 12.

The secondary efficacy endpoints are the following:

- 1) Proportion of subjects achieving a lesion count of 0 or 1 of all treatable MC at Week 12.
- 2) Proportion of subjects achieving at least a 90% reduction from Baseline in the number of all treatable MC at Week 12.
- 3) Proportion of subjects with complete clearance of all treatable MC at Week 8.
- 4) Percent change from Baseline in the number of all treatable MC at Week 4.

Complete clearance is defined as having a total number of lesions count of 0.

The exploratory endpoints are the following:

- Percent change from Baseline in number of treatable MC at each visit (Weeks 2, 8, 12)
- Proportion of subjects achieving a lesion count of 0 or 1 of all treatable MC at Weeks 2, 4, and 8
- Proportion of subjects achieving at least a 90% reduction from Baseline in the number of all treatable MC at Weeks 2, 4, and 8
- Proportion of subjects achieving at least a 75% reduction from Baseline in the number of all treatable MC at Weeks 2, 4, 8, and 12
- Absolute change from Baseline in number of treatable MC at Weeks 2, 4, 8, 12
- Proportion of subjects with complete clearance of all treatable MC at Week 2 and Week 4 visits
- Time to complete clearance of all treatable MC, defined as the days between the date of first dose and the first date of clearance. Subjects who do not achieve complete clearance will be censored at the date of the last lesion count assessment.
- Proportion of subjects who have a recurrence of MC after the first visit at which complete clearance was observed, defined as the total lesion count being greater than 0 at any point after achieving a count of 0
- Subject-reported spread to household members as measured by any new occurrence of MC in household members of subjects at each visit (Weeks 2, 4, 8, 12)
- Investigator Global Severity Assessment at Baseline, Week 12, and Week 24
- Subject Global Severity Assessment at Baseline, Week 12, and Week 24
- Investigator Global Impression of Change at Week 12 and Week 24

- Subject Global Impression of Change at Week 12 and Week 24

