Subjects or their caregivers will apply SB206 10.3% or Vehicle Gel once daily for a minimum of 4 weeks and shall continue unless otherwise instructed by the investigator up to 12 weeks to all lesions identified at Baseline and new treatable lesions that arise during the course of the study. Subjects or their caregivers will continue to treat the area until the next scheduled visit even if the lesion(s) clear. At each in-clinic and remote visit, the investigator will count and record the number of active (raised, treatable) molluscum lesions per body area. Complete clearance should be confirmed by an in-clinic lesion count before treatment is discontinued. If the investigator determines all lesions are cleared at a visit, the investigator may instruct the subject to stop treatment. If treatment is stopped due to clearance, subjects will continue regularly scheduled visits through Week 12/ET and all procedures outside of study drug activities should be continued. If lesions recur or new lesions occur between visits after being stopped due to clearance, the subject or caregiver should re-initiate treatment to the recurring and new lesions. A new kit should be dispensed at Weeks 4 and 8 regardless of lesion count so that treatment can be restarted if lesions are observed between visits. An unscheduled visit is not required for the subject/caregiver to resume treatment. No study treatment is planned to be dispensed after the Week 12 visit.

Remote visits may be performed at Week 4 using remote technology. During the Baseline visit, the subject/caregiver will be instructed on the technology to be used for remote visits. After the initial molluscum lesion count is completed, it will be repeated by the same assessor and the subject/caregiver using the subject/caregiver's electronic device that will be utilized to capture photographs for remote visits. This will provide the subject/caregiver an opportunity to practice with the technology and will allow for the assessor to understand lesion appearance in person compared to through the technology platform.

Subjects will be contacted via phone on Day 2 to collect subject information on early dose reactions. At Weeks 16 and 20, subjects will be contacted via phone to capture information regarding MC recurrence and adverse events (AEs); at Week 24, the subject will be seen at the site for a final study visit to assess scarring, keloid, and MC recurrence.

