6.4 Remote Visits

Week 4 can be performed as a remote visit or in clinic visit. All subjects/caregivers will be instructed on the technology to be utilized during the Baseline visit. Approximately 24-48 hours in advance of the remote visit, the subject or caregiver should utilize the historic lesion map to

take images of all lesion areas noted at the previous visit and any new lesion areas that developed since the previous visit. Photographs of the lesions should be taken prior to IP application for the day or at least 1 hour after application. The remote visit should be rescheduled within visit window if acceptable images have not been received by the site. Additional instructions on how to take and upload photographs is provided in the Study Reference Manual.

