7.1 Efficacy Assessments

7.1.1 Molluscum Contagiosum Lesion Counts

Molluscum contagiosum is a viral infection characterized by small, discrete, waxy, skin-colored, dome-shaped raised papules, an average of 3–5 mm in diameter. The papules may be umbilicated and contain a caseous plug. When the lesions are squeezed or traumatized, a creamy, grey-white material can be extruded. If the investigator cannot clearly differentiate the lesions as is the case for agminated (clustered) lesions this should be counted as one lesion. If the investigator can differentiate and count the umbilical tops separately, each lesion should be counted separately. The investigator should be consistent with the method of recording agminated lesions throughout the study.

For the purpose of this clinical trial, only treatable MC lesions are counted. Treatable lesions are any active (raised, palpable) MC lesions that are dome-shaped, pearly, and shiny white top centered papules that are at least 2 cm away from the ocular region. In clinic, investigators may choose to palpate the lesion to confirm if it is raised. Treatable region is any skin area containing a molluscum lesion, with the exception of the periocular region.

All study personnel who will perform lesion counts must pass the study training including lesion count training. Training on how to accurately count the number of MC lesions will be provided.

Mapping of lesions: At every visit from Baseline through Week 12, all lesions should be recorded on the body map and will clearly note the location of each lesion or agminated lesion. The lesion map is intended to assist study personnel in performing lesion counting and scar/keeloid assessment. The body map will also be shared with the subjects/caregivers at Week 2 to assist with counting of lesions.

Definition of Clearance: For the purpose of this study, “clear” means resolution of the active (raised, palpable) treatable molluscum lesion(s). After a lesion has cleared, the residual surface changes such as a pitted scar (indentation), hyperpigmentation, or hypopigmentation may remain. Additional details will be provided in the lesion count training. Complete clearance can only be confirmed by an in-clinic lesion count.

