10.3 Testing Procedures

10.3.1 Analysis of the Primary Efficacy Endpoint

The primary efficacy endpoint for this study is the proportion of subjects achieving complete clearance of all treatable molluscum lesions at Week 12 for the ITT population. Complete clearance of all MC at Week 12 is defined as having a lesion count of 0 at Week 12. The number and percentage of subjects with complete clearance at Week 12 will be summarized by treatment group.

The primary efficacy endpoint will be analyzed using a generalized estimating equation (GEE) for logistic regression with an exchangeable working correlation structure. The model will include treatment, investigator type (dermatologist vs other), Baseline BOTE score (no inflammation (BOTE = 0) vs. mild/moderate/severe inflammation (BOTE \geq 1) and number of randomized subjects per household (1 subject per household vs. 2 subjects per household), age and Baseline lesion count as factors. The odds ratio between SB206 10.3% and vehicle gel, 95% CIs for the odds ratio, and P-value for the covariate-adjusted treatment comparison will be presented; together with predicted proportions along with their associated 95% confidence interval. Only subjects who achieve complete clearance at Week 12 will be counted as responders for the primary analysis. Subjects who discontinue the study before the Week 12 analysis visit for any reason will be considered not to have achieved complete clearance at Week 12, even if the subject discontinues after a lesion count of 0.

As a sensitivity analysis, the primary efficacy analysis will also be applied to the PP population. Additional sensitivity analyses may be performed including analyses that utilize alternative assumptions from those of this primary method to ensure that efficacy results are not driven by the method of handling missing data.

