- If the subject did not have a Week 12 lesion count assessment and the response to the disease status was ‘Resolved (no lesions left)’ or ‘Resolving (number of lesions decreasing)’, then the subject will be deemed a responder.
- Otherwise, the subject will be deemed a non-responder.

The sensitivity analysis of this patient reported response will be analyzed in the same manner as the primary endpoint. A list of the patient reported outcome of MC disease status will be provided.

A sensitivity analysis on the manner of assessment of lesion counts at Week 12 (in-clinic vs. remote) may be performed where subjects with only a remote assessment will be counted as non-responders.

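### A remote count of zero can stand as complete clearance, mainly at Week 4, although Protocol 7.1.1 reserves confirmation of clearance to an in-clinic count

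*SAP*

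**What the plan says.** Protocol 7.1.1, in its definition of clearance, says that "Complete clearance can only be confirmed by an in-clinic lesion count". Protocol 4.1 and SAP 4 also call for in-clinic confirmation, but in the context of stopping treatment.

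The analysis sections do not carry this condition. Protocol 10.3.1: "Complete clearance of all MC at Week 12 is defined as having a lesion count of 0 at Week 12". SAP 10.1: "Complete clearance is defined as having a total number of lesions count of 0". The derived endpoints in SAP 10.1 inherit that definition. Time to clearance is "defined as the days between the date of first dose and the first date of clearance", and recurrence is "defined as the total lesion count being greater than 0 at any point after achieving a count of 0".

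Remote counts are planned and recorded as data. Protocol 6.4: "Week 4 can be performed as a remote visit or in clinic visit". Those reads use photographs taken by the subject or caregiver.

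The SAP has two rules on how a post-baseline count was made:
- SAP 7: where remote and in-clinic counts fall in the same window, the in-clinic count is analysed.
- SAP 10.4: an optional Week 12 sensitivity analysis "where subjects with only a remote assessment will be counted as non-responders".

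SAP 10.2 fixes the in-clinic count for baseline. SAP 14 declares no modification or clarification of the protocol's methods.

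**The concern.** Protocol 7.1.1 defines clearance as resolution of raised, palpable lesions. A lesion can be palpated in clinic but not in a photograph, so the restriction to in-clinic confirmation has a clear purpose. As the SAP is written, a zero that Protocol 7.1.1 would not accept as confirmed can still be analysed as complete clearance.

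The outputs at stake are the Week 4 clearance proportion, the event dates in the Kaplan-Meier analysis and its stratified log-rank test (SAP 11.3), the recurrence proportion, and the planned analyses in SAP 10.4 and 11.1 that count a subject without a Week 12 count as a responder if the last assessment showed clearance. Those last analyses support the primary result, and a remote Week 4 zero followed by dropout would count as a success in them. If the choice stays open, it could be settled after the treatment codes are known.

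**Working it through.** **1. Following one subject through the rules.** Take a subject with a remote Week 4 visit on Day 29, a count of 0, and no in-clinic count in the Week 4 window (Day 23 to 43 in SAP 7).

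| Output | SAP as written | With the Protocol 7.1.1 condition |
|---|---|---|
| Week 4 complete clearance | Yes | Not confirmed |
| Time to clearance, Week 8 in-clinic count 0 | Event at Day 29 | Event at Day 57 |
| Time to clearance, Week 8 in-clinic count above 0 | Event at Day 29 | No event yet |
| Recurrence, Week 8 in-clinic count above 0 | Yes | No, clearance never confirmed |
| Last-assessment sensitivity analysis, no later count | Responder | Non-responder |

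The shift in event date is 57 − 29 = 28 days on target days. With the ±5-day visit windows it runs from 52 − 34 = 18 to 62 − 24 = 38 days. An unscheduled in-clinic check would shorten it.

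**2. What the window rule covers.** An in-clinic count between Day 23 and Day 43 displaces the remote one in the by-visit analysis. The SAP does not say whether this also governs the first clearance date in the time-to-event analysis.

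**3. Routes into the Week 12 endpoint.** Week 12 is planned in clinic (Protocol 6.3, 6.7.7). A remote early-termination visit needs sponsor approval (Schedule of Assessments footnote) or discussion with the medical monitor (Protocol 6.8.3), and remote unscheduled visits are allowed. SAP 7 can assign an early-termination count, or an unscheduled count where the visit has none, to Week 12 if it falls in Day 72 to 98. Against this, Protocol 10.3.1 makes subjects who discontinue before the Week 12 analysis visit non-responders, even after a zero count.

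**4. Scale for the primary endpoint.** First the plan's own figure. Inputs from SAP 5: n = 425 per arm, 20% vehicle (V), 29.5% SB206 (S), two-sided alpha 0.05.

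Power = Φ[(d − 1.96·√(2p̄(1−p̄)/n)) / √((pV(1−pV) + pS(1−pS))/n)]

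With d = 0.095 and p̄ = 0.2475: (0.095 − 1.96 × 0.0296)/0.0294 ≈ 1.26, so power is 89.6%. This agrees with the stated 90% and lies within 2 points of the SAP's simulated 88%.

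Now let a share r of Week 12 zeros be remote-only and recode them as non-response, so that each rate is multiplied by (1 − r). The share r is an assumption, taken as equal in both arms.

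| r | Vehicle | SB206 | Difference (points) | Subjects recoded | Power |
|---|---|---|---|---|---|
| 0% | 20.0% | 29.5% | 9.5 | 0 | 89.6% |
| 1% | 19.8% | 29.2% | 9.4 | 2.1 | 89.2% |
| 5% | 19.0% | 28.0% | 9.0 | 10.5 | 87.5% |
| 10% | 18.0% | 26.55% | 8.55 | 21.0 | 85.1% |

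Subjects recoded = 425 × r × (0.20 + 0.295). Unequal shares would matter more: 5% in the SB206 arm alone gives 8.0 points and 78.3% power, and 5% in the vehicle arm alone gives 10.5 points and 94.8%. The documents give no reason to expect an imbalance, and assessors are blinded (Protocol 8.5).

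**5. Scale at Week 4.** No calculation is possible. The documents give neither the share of Week 4 visits held remotely nor a Week 4 clearance rate in the text.

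**The case against.** The strongest reply is that the SAP follows the protocol's own analysis section. Protocol 10.3.1 has no condition on how the count is made, and the wording in Protocol 4.1 concerns when treatment may stop. This stands in part: the protocol disagrees with itself, so this is not simply the SAP departing from it. But Protocol 7.1.1 places its sentence in the definition of clearance and does not confine it to treatment decisions. The conflict remains.

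It is also fair to say that what is routinely exposed is exploratory. Week 4 clearance, time to clearance and recurrence lie outside the fixed testing sequence. Week 8 clearance is planned in clinic, and the Week 4 secondary endpoint is a percent change that needs no definition of clearance. That limits the importance of the point. It does not cover the last-assessment analyses, which bear on the primary result and are planned rather than optional.

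Three stronger readings are tempting, and the documents do not support them:
- *Every remote zero counts as clearance.* The SAP 7 priority rule replaces it when an in-clinic count lies in the same window.
- *Remote zeros routinely enter the primary endpoint.* The route is exceptional, and the non-responder rule for early discontinuers closes most of it.
- *Week 4 clearance is inflated by a known fraction.* One percent of 850 is 8.5 subjects, or one percentage point, but that is an identity. Calling it a 20 to 33% inflation requires an assumed Week 4 rate of 3 to 5% and treats every unconfirmed zero as false.

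**Conclusion.** The point holds as an unresolved definition. Protocol 7.1.1 conflicts with Protocol 10.3.1 and SAP 10.1, and no other rule in the SAP settles a sole remote zero. The optional Week 12 analysis in SAP 10.4 shows that the main analysis does not exclude one. The routine effect is confined to the optional remote Week 4 visit and the outputs traced above. Its size is unknown, and no bias in the treatment comparison is shown. For the primary endpoint the effect should be small, provided that remote-only Week 12 counts are rare and similar in both arms. The planned power itself is not in dispute. This should be corrected before unblinding, but it is not a reason to doubt the primary analysis.

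**What to change.** Before unblinding, reconcile Protocol 7.1.1, Protocol 10.3.1 and SAP 10.1:

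- In SAP 10.1, state that complete clearance requires an in-clinic total count of 0.
- For time to clearance and recurrence, date clearance at the first in-clinic zero.
- In the last-assessment sensitivity analyses (SAP 10.4 and 11.1), do not treat a remote-only zero as clearance.
- Report Week 4 clearance under the any-mode definition as a sensitivity analysis.
- At Week 12, make the remote-only rule of SAP 10.4 the main rule. If any-mode counting is kept there, make the SAP 10.4 analysis mandatory and declare the choice in SAP 14.

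The cost is SAP wording and some programming, since SAP 7 already distinguishes the type of assessment. There are two drawbacks. Some clearance dates move to the next in-clinic visit, about 28 days later on target days. Week 4 clearance becomes conservative for subjects seen remotely: the same remote zero would still be a response for 0-or-1 lesions and for the 90% and 75% reductions at Week 4. The SAP should state this so that the tables are not read as inconsistent.

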6.7.7 Visit 6/Week 12/ET (Day 85 ±5 days) (In-clinic Visit)

The following procedures must be performed and recorded at the Week 12/ET visit.

1. Obtain pregnancy test and evaluate results, as applicable.
2. Perform BOTE Inflammation Score.
3. Perform Local Skin Reaction Assessment.
4. Perform lesion counts and update lesion map with location for any new lesions.
5. If previously cleared, assess for subject recurrence of MC.
6. Perform scarring/keloid assessment; if present, document location on lesion map and record as an AE.

7. Perform a brief physical examination.
8. Complete Investigator Global Severity Assessment and Investigator Global Impression of Change Assessment.
9. Complete Subject Global Severity Assessment and Subject Global Impression of Change Assessment.
10. Subject/caregiver administer final dose of study drug from previously dispensed kit only if lesions are present.
11. Weigh returned study drug and review study compliance.
12. Collect and record AE information for AEs reported.
13. Update concomitant medication information and confirm if any new occurrences of MC were reported in the subject's household.
14. Review interview procedures with the subject/caregiver and obtain documented ICF/assent.

Note: Follow up interviews will be performed with a subset of subjects that complete Week 12. Consent will be obtained during the Week 12 visit, and the follow up interview will be performed with the subject/caregiver at a later date.

**6.7.8 Visit 7/Week 16 and Visit 8/Week 20 (Day 113 ±7 days; Day 141 ±7 days)
(Telephone Contact)**

The following procedures must be performed and recorded at the Week 16 and Week 20 visits. It is expected that these visits should be done by telephone.

1. Collect and record information for new and ongoing AEs, including recurrence of MC.
2. Confirm household MC status (any new cases in household members since last visit).
3. Update concomitant medication information.

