6.7.9 Visit 9/Week 24 (Day 169 ± 7 days) (In-clinic Visit)

The following procedures must be performed and recorded at the Week 24 visit.

1. Perform scarring/keloid assessment; if present, document location on lesion map and record as an AE.
2. Complete Investigator Global Severity Assessment and Investigator Global Impression of Change.
3. Complete Subject/Caregiver Global Severity Assessment and Subject Global Impression of Change.
4. Collect and record information for new and ongoing AEs, including subject recurrence of MC.
5. Confirm household MC status (any new cases in household members since last visit visit).
6. Update concomitant medication information.

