7.2.6 Adverse Events

Adverse events will be assessed and collected after the initiation of study drug treatment through the end of the subject's last visit. Treatment-related adverse events and serious adverse events will be followed up until resolution or up to one year after last treatment, whichever occurs earlier.

If a subject's treatment is discontinued by the investigator or the subject because of an AE, that AE should be indicated as the reason for treatment discontinuation. All subjects will be encouraged to remain in the study and to complete all required study visits throughout the 24-week study duration.

If a subject achieves complete clearance at Week 12 or before and experiences new lesions between Week 12 and Week 24, an AE of molluscum contagiosum should be documented to capture this recurrence since there is no lesion count after Week 12.

See [Section 9](#) for additional information regarding adverse events.

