Subjects or their caregivers will apply SB206 10.3% or Vehicle Gel once daily for a minimum of 4 weeks and shall continue unless otherwise instructed by the investigator up to 12 weeks to all lesions identified at Baseline and new treatable lesions that arise during the course of the study. Subjects or their caregivers will continue to treat the area until the next scheduled visit even if the lesion(s) clear. At each in-clinic and remote visit, the investigator will count and record the number of active (raised, treatable) molluscum lesions per body area. Complete clearance should be confirmed by an in-clinic lesion count before treatment is discontinued. If the investigator determines all lesions are cleared at a visit, the investigator may instruct the subject to stop treatment. If treatment is stopped due to clearance, subjects will continue regularly scheduled visits through Week 12/ET and all procedures outside of study drug activities should be continued. If lesions recur or new lesions occur between visits after being stopped due to clearance, the subject or caregiver should re-initiate treatment to the recurring and new lesions. A new kit should be dispensed at Weeks 4 and 8 regardless of lesion count so that treatment can be restarted if lesions are observed between visits. An unscheduled visit is not required for the subject/caregiver to resume treatment. No study treatment is planned to be dispensed after the Week 12 visit.

Remote visits may be performed at Week 4 using remote technology. During the Baseline visit, the subject/caregiver will be instructed on the technology to be used for remote visits. After the

initial molluscum lesion count is completed, it will be repeated by the same assessor and the subject/caregiver using the subject/caregiver's electronic device that will be utilized to capture photographs for remote visits. This will provide the subject/caregiver an opportunity to practice with the technology and will allow for the assessor to understand lesion appearance in person compared to through the technology platform.

Subjects will be contacted via phone on Day 2 to collect subject information on early dose reactions. At Weeks 16 and 20, subjects will be contacted via phone to capture information regarding MC recurrence and adverse events (AEs); at Week 24, the subject will be seen at the site for a final study visit to assess scarring, keloid, and MC recurrence.

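### The recurrence endpoint uses lesion counts only, but none is scheduled after Week 12, so recurrences recorded as adverse events up to Week 24 are left out of it

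*SAP*

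**What the plan says.** - **Definition.** SAP 10.1 lists the proportion of subjects with recurrence after first complete clearance, "defined as the total lesion count being greater than 0 at any point after achieving a count of 0". SAP 11.3 says only that it will be summarized. Neither names another data source, a time limit or a denominator. The output is Table 14.2.3.7 (ITT).
- **Counts.** The Schedule of Assessments (Protocol Table 1) has lesion counts up to Week 12/ET1 and none at Weeks 16, 20 or 24.
- **Substitute record.** For subjects clear at Week 12 or before who develop new lesions between Weeks 12 and 24, Protocol 7.2.6 says "an AE of molluscum contagiosum should be documented to capture this recurrence since there is no lesion count after Week 12".
- **Follow-up contacts.** At the Week 16 and 20 telephone contacts (Protocol 6.7.8) the task is to "Collect and record information for new and ongoing AEs, including recurrence of MC". The Week 24 clinic visit (6.7.9) has nearly the same item and no lesion count. SAP section 4 itself says that at Week 24 "the subject will be seen at the site for a final study visit to assess scarring, keloid, and MC recurrence".
- **Where those AEs go.** SAP 13.1 summarizes post-treatment AEs by system organ class and preferred term in the Safety Population. Appendix C adds a listing (16.2.7.4).
- **Declared changes.** SAP section 14 reports no modification or clarification of the protocol's methods. The protocol's own endpoint (sections 3 and 10.3.6) is not limited to counts or to Week 12.

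**The concern.** The protocol recognises that counts stop at Week 12 and provides another way to record later recurrence. The SAP definition does not use it. Two things follow:

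1. A recurrence reported at Week 16, 20 or 24 is not an event for the endpoint.
2. A subject first clear at Week 12 has no later scheduled count and so cannot become an event at any scheduled visit.

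The stake is what the trial can say about durability. Before Week 12, subjects who stopped because they had cleared are told to resume treatment if lesions return. No study drug is planned after Week 12. Weeks 12 to 24 are therefore the planned off-treatment period for everyone, and the recurrence endpoint takes no scheduled information from it. A low figure in Table 14.2.3.7 could be read as durable clearance when it partly reflects that nobody was counting.

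**Working it through.** **1. Can a scheduled visit produce an event?** An event needs a count of 0 followed by a later count above 0. Scheduled post-baseline counts are at Weeks 2, 4, 8 and 12.

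| First count of 0 | Later scheduled counts | Later AE-based recurrence records |
|---|---|---|
| Week 2 | Weeks 4, 8, 12 | Weeks 16, 20, 24 |
| Week 4 | Weeks 8, 12 | Weeks 16, 20, 24 |
| Week 8 | Week 12 | Weeks 16, 20, 24 |
| Week 12 | none | Weeks 16, 20, 24 |

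The endpoint uses the middle column only.

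**2. The plan's own design figure.** The endpoint has no stated figure. The planned Week 12 rates (20% vehicle, 29.5% SB206, 425 per arm; SAP section 5) are used in step 4, so I checked them. Power = Φ{[0.095·√425 − 1.96·√(2·0.2475·0.7525)] / √(0.20·0.80 + 0.295·0.705)} = Φ{(1.958 − 1.196)/0.607} = Φ(1.257) = 89.6%. The stated 90% reproduces and is not in dispute.

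**3. How many Week 12 responders were not recorded as clear at Week 8?** Inputs are the Week 8 and Week 12 clearance rates of the two earlier phase 3 studies (Protocol 2.1.4.3). No more subjects can be clear at both visits than are clear at Week 8, so the share is at least (Week 12 rate − Week 8 rate) / Week 12 rate.

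| Study, arm | Week 8 | Week 12 | Minimum share |
|---|---|---|---|
| NI-MC301 SB206 | 15.3% | 25.8% | 10.5/25.8 = 40.7% |
| NI-MC302 SB206 | 13.9% | 30.0% | 16.1/30.0 = 53.7% |
| NI-MC301 vehicle | 10.3% | 21.6% | 11.3/21.6 = 52.3% |
| NI-MC302 vehicle | 5.9% | 20.3% | 14.4/20.3 = 70.9% |

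**4. Scale in this trial.** Subjects clear at Week 12 at the planned rates: 425 × 0.295 = 125 SB206 and 425 × 0.20 = 85 vehicle. Carrying over the earlier Week 8 rates:
- SB206 clear at Week 8: 425 × 0.139 = 59 to 425 × 0.153 = 65, leaving at least 60 to 66 not recorded as clear then.
- Vehicle clear at Week 8: 425 × 0.059 = 25 to 425 × 0.103 = 44, leaving at least 41 to 60.

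**5. Recurrences that would be missed.** The documents give no recurrence rate after Week 12. Assuming 5%, 10% or 20% of all Week 12 clear subjects, for illustration only, the endpoint would miss about 6, 13 or 25 SB206 recurrences (125.4 × rate) and 4, 9 or 17 vehicle recurrences (85 × rate).

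**The case against.** The strongest reply is that the events are reported, only elsewhere. The protocol deliberately routes later recurrence to AEs, and the SAP tabulates post-treatment AEs by arm, preferred term and severity and lists them. The investigator's Week 24 global severity rating, which has a category for no disease, appears in a shift table. So a reader might infer that post-Week-12 recurrences are lost altogether, and the documents do not support that. What stands is that those tables use the Safety Population and do not give a proportion of cleared subjects.

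A reader might also infer the following, each too strong:

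- **That a subject first clear at Week 12 can never be counted.** Unscheduled visits are permitted, including for lesion clearance (notes to Protocol Table 1), and the SAP section 7 windows run to Day 182. A later count is possible, but none is planned.
- **That 41% to 71% of the endpoint's denominator is affected.** The SAP names no denominator for this endpoint; its section 6 default is all subjects in the population. The bound in step 3 concerns Week 12 responders, whereas the relevant group is subjects ever cleared. Missing counts were scored as not clear (notes to Protocol Figures 2 and 3), so some of these subjects may already have been clear at Week 8. Subjects clear at Week 2 or 4, not at Week 8 and clear again at Week 12 would count as recurrences.
- **That vehicle is understated more than SB206.** Using the Safety Population sizes in Protocol Table 2 as approximate denominators, the pooled counts clear at Week 8 and Week 12 are about 69 and 132 (SB206) and 19 and 49 (vehicle). Not clear at Week 8: 63/132 = 47.7% and 30/49 = 61.2%. If Week 8 clearers are treated as a subset of Week 12 clearers, the difference is 13.5 points with standard error √[0.514 × 0.486 × (1/132 + 1/49)] = 8.4 points, so z = 1.61 and p is about 0.11. That does not settle a difference in timing, and recurrence rates after Week 12 are unknown.

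Finally, a count-only measure by trained evaluators through Week 12 is a legitimate quantity, and mixing it with telephone reports has a cost. That argues for labelling and separate reporting, not for leaving the definition open-ended.

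**Conclusion.** The point holds for the endpoint and for Table 14.2.3.7. Followed as written, the SAP omits the recurrences that the protocol arranges to record between Weeks 12 and 24 and gives subjects first clear at Week 12 no scheduled opportunity for an event. As a measure of recurrence during the study, the proportion is biased low in each arm, provided that some recurrences occur after Week 12.

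The bounds from the earlier studies show that the affected group may be large. They assume that clearance timing here resembles those studies, and they cover only Week 12 responders not recorded as clear at Week 8. Follow-up after clearance may differ by arm, but the size and direction of any between-arm distortion cannot be derived from the documents.

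The consequence is limited. The endpoint is exploratory, descriptive and outside the testing hierarchy, so no power figure, significance level or primary conclusion changes.

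**What to change.** Amend SAP 10.1, 11.3 and Table 14.2.3.7 before the Week 12 database is unblinded, since SAP section 6 classes analyses performed after that as post hoc:

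- **(a)** Keep the count-based figure, label it as recurrence through Week 12, and limit its denominator to subjects with a count of 0 and at least one later lesion count.
- **(b)** Add recurrence through Week 24: a lesion count above 0, or an AE of molluscum contagiosum with onset after first clearance, among cleared subjects with any later follow-up. Report it separately from (a).

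The cost is SAP wording and one additional display; the data are already collected. The downside is that the Week 24 figure combines investigator counts with AE reports, some taken by telephone, and its label should say so.
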